5.4.1 Subject personal experience

Subjects will assess the treatment improvement using the GAIS (Global Aesthetic Improvement Scale).

5.4.2 Study termination CRF:

The termination CRF should be completed with the PI signature.

6 Endpoint Evaluations

The primary efficacy endpoint will be improvement in treated area appearance at 6 weeks after the last treatment as determined by an independent review using the GAAS.

The secondary endpoints include: subject satisfaction & subjects' assessment of improvement as well as subjects' assessment of discomfort with the procedure, subject's "Quality of Life", lesion count, and efficacy comparison of combination treatment and IPL treatment alone.

6.1 Efficacy

6.1.1 Global Acne Assessment Score:

In the first step, independent reviewers will receive 2 photographs for each client (visits 5 and 6 and an archival photograph taken at baseline) and they will need to determine which photograph represents "before" picture and which represents the "after" picture. Once this step is completed, in the next step the independent reviewers will grade the improvement by comparing the before and after photographs according to the GAAS.

6.1.2 Lesion Count (Face):

Lesion counts including inflammatory lesions and non-inflammatory lesions will be performed at visits. The lesion counts will be performed on the entire face, including the nose, and will be evaluated by the investigator or an appropriately trained designee. Facial inflammatory lesions (pustules, papules, and nodular lesions) and non-inflammatory lesions (open and closed comedones) will be counted and recorded separately.

The following lesion types will be evaluated:

- Inflammatory lesions
 - Papule – a small, red, solid elevation less than 1.0 cm in diameter
 - Pustule – a small, circumscribed elevation of the skin that contains yellow-white exudate
 - Nodule/cyst – a circumscribed, elevated, solid lesion generally more than 1.0 cm in diameter with palpable depth
- Non-inflammatory lesions
 - Open comedone – a pigmented dilated pilosebaceous orifice (blackhead)
 - Closed comedone – a tiny white papule (whitehead)

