3.1 Primary effectiveness endpoint

- Improvement in treated area appearance at 6 weeks after the last treatment as determined by a independent review.

Success criterion

The treatment will be considered successful if the appearance of Acne Vulgaris improves by at least 2 points on the 5-point Global Acne Assessment Score (GAAS) at 6 weeks follow-up compared to baseline in the study population. This will be determined by calculating the mean difference $GAAS-(\mu_d)$ between the GAAS at 6 weeks follow-up and the baseline scores in the study population. This improvement will also be further tested by two-sided Wilcoxon Signed-Ranks Test for Matched Pairs to establish that at 95% confidence level ($\alpha = 0.05$) there is a statistical significant evidence that mean difference scores obtained (μ_d) is not equal to zero.

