3.7 Blinding

Objective assessment of clinical improvement by GAAS will be achieved by sending before/after pictures (baseline/prior to last treatment/6 weeks after last treatment) to up to 3 independent reviewers at the end of the study. The reviewers will not know which are the before and which are the after pictures.

4 Study Population and Subject Selection

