5.1.2 Subject Identification

At enrollment, each subject will receive a unique identifying number that will be composed of the site number and a consecutive number with his/her initials. This unique identifier will be used throughout the entire study and will be entered in the subject's CRF for each treatment and photographs. Photographs will be stored on a secure computer that is password protected and they will be labeled and numbered by date with the patient ID only.

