5.3.1 Photography: see section 5.2.1.2

5.3.2 Improvement assessments

5.3.2.1 GAAS and Lesion Count

Up to three independent reviewers will be required to evaluate the Acne Vulgaris grading using the GAAS based on before/after photos of baseline/6 weeks following the last Tx and to perform lesion count. The independent evaluators will not know which the baseline are and which the FU photos are.

The principal investigator or an appropriately trained designee will perform a lesion count at all visits.

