7.1 Statistical and Analytical Plans

This is the basis for the Statistical Analysis Plan for this study. This plan may be revised during the study to accommodate amendment to this Protocol and to make changes in relation to unexpected issues in study execution and data that affect planned analyses. Revisions to this protocol will be based on independent review of the study data and a final plan will be issued prior to data lock.

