7.4 Study Analysis

- All subjects will be evaluated for efficacy and safety data at baseline, during treatments and at 6-week post treatment visit.
- The analysis set will be as complete as possible and as close as possible to ensure it complies with the intent-to-treat principle for all enrolled subjects
- Subject demographics, baseline assessments, treatment parameters, treatment evaluations, follow-up assessments and reported adverse events will be summarized and analyzed using the following statistical tools:
 - All summary tables for quantitative parameters will display mean, standard deviation, median and applicable descriptive statistics. Correlations between variables will also be performed where applicable.
 - All summary tables for qualitative parameters will show counts, percentages and orders.
 - Number of missing data will be displayed on all tables where applicable.
 - Inter-rater reliability test will be performed to assess agreement between reviewers.
 - All statistical tests will be two-sided. The level of statistical significance for effectiveness analyses is 5% ($\alpha = 0.05$) for all tests of differences. Paired t-test and/or Wilcoxon Signed-

Ranks Test for Matched Pairs will be used to compare the evaluations at the baseline and post treatment sessions.

- For all primary and secondary end-point data generated in this study, applicable data analysis tools listed above will be used to determine if the study meets its efficacy and safety criteria.

8 Adverse Events

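### Section 6.1.1 has reviewers order the photographs and then grade improvement, whereas 3.1 needs a GAAS score at each time point; no rule covers a wrongly ordered pair.

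*Combined protocol and SAP*

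**What the plan says.** - **Section 3.1** takes the mean difference "between the GAAS at 6 weeks follow-up and the baseline scores in the study population", asks for at least 2 points on the 5-point scale, and adds a two-sided Wilcoxon signed-rank test against zero at 0.05.
- **Section 7.4** says that a paired t-test and/or the signed-rank test "will be used to compare the evaluations at the baseline and post treatment sessions".
- **Section 5.3.2.1** has up to three independent reviewers grade acne on the GAAS from baseline and 6-week photographs: "The independent evaluators will not know which the baseline are and which the FU photos are". It does not say whether each photograph is scored alone.
- **Section 3.7** gives the same masking: "The reviewers will not know which are the before and which are the after pictures".
- **Section 6.1.1** has two steps. Reviewers first work out which photograph is the earlier and which the later. Then: "Once this step is completed, in the next step the independent reviewers will grade the improvement by comparing the before and after photographs". It speaks of two photographs but lists three time points (baseline, visit 5, visit 6).
- **The Synopsis, Table 1 (section 3.5) and the opening of section 6** also describe the reviewers' GAAS result as improvement. Table 1 marks it at follow-up only.
- **Section 7.1** allows revision of the analysis plan and says that "a final plan will be issued prior to data lock".

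**The concern.** A difference of two severity scores and a comparative improvement grade are different measurements. The second takes its direction from whichever photograph the reviewer believes came first. A reviewer who expects treatment to work may sort by severity and call the clearer face the later one. A subject who got worse is then recorded as having improved.

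The text leaves open whether such a pair keeps its grade, has its sign restored, is set to zero, or is excluded. It also leaves open whether reviewers learn the true order between the two steps. If they do, sorting errors no longer matter, but the masking promised in 3.7 and 5.3.2.1 is lost at the grading step.

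The independent-review GAAS is the only primary endpoint, so the reported effect size and its supporting test both rest on this procedure.

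**Working it through.** **1. Text check.** Sections 3, 3.1, 3.5, 3.7, 5.3.2.1, 6.1.1 and 7.1 to 7.4 contain no rule for a wrong order and no statement on disclosure. The only analysis of the reviewers' readings as such is the agreement test in 7.4. The protocol gives no power calculation, SD or mis-sorting rate, so there is no planned figure to reproduce. What follows is an illustration on assumed inputs.

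**2. Set-up.** One grade per subject, kept in the reviewer's order. There is no average change. A share p of pairs differs by one grade, half better and half worse. Let m_w and m_i be the shares of worsened and improved pairs that are mis-sorted, and d = m_w − m_i.

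- Chance that a non-zero pair is recorded as improvement: 0.5(1 − m_i) + 0.5 m_w = 0.5 + 0.5d.
- Spurious mean gain: p × [2(0.5 + 0.5d) − 1] = p × d.
- All non-zero differences are +1 or −1, so the exact signed-rank test equals the exact sign test. With k ~ Bin(n, p) non-zero pairs and Bin(k, 0.5 + 0.5d) positives given k, the rejection rate is the sum over k of P(k) × P(two-sided sign test rejects at 0.05 | k).

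**3. Choice of n.** The Synopsis aims for 20 completers under the amendment 2 parameters, out of up to 50 enrolled. Section 7.4 leans towards all enrolled subjects. The primary objectives are stated per treatment, so n=10 is one arm of 20 under an even split, which is an assumption. I show all three.

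**4. Results** for p = 0.3 to 0.7:

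| d | Spurious gain (grades) | n=10 | n=20 | n=50 |
|---|---|---|---|---|
| 0 | 0 | 0.1%–1.8% | 1.3%–2.6% | 2.8%–3.3% |
| 0.5 | 0.15–0.35 | 0.8%–13.8% | 9.9%–37.2% | 40.7%–82.6% |
| 1 | 0.30–0.70 | 4.7%–85.0% | 58.4%–100% | 99.9%–100% |

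The d=0 row also gives the rates when the true order is used. At n=20, rejection passes the nominal 5% only once d exceeds about 0.15 (p=0.7) to 0.35 (p=0.3).

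**5. The 2-point rule,** simulated at n=20 with rounded normal changes and every worsened pair reversed:

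- No true change, SD 0.5 to 1.0: apparent mean gain 0.32 to 0.76. A mean of 2 or more occurred in 0 of 20,000 trials.
- True gain 1.0, SD 0.8 to 1.2: 0.06 to 0.25 grade added. The chance of meeting the rule stays below 0.1%.
- True gain 1.5, same SDs: 0.01 to 0.11 grade added. That chance moves from 0.6%–3.8% to 0.7%–6.2%.

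**The case against.** The best defence is that the sections can be read together. Grading according to the GAAS may mean that each photograph receives a GAAS grade while the two are compared. Section 3.1 then takes the difference by actual visit, and a sorting error cannot change the sign. This reading is available and would remove the bias. But 6.1.1 says that improvement is what gets graded, and no sentence tells the analyst to return to actual visits.

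Several limits also stand:

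- Section 3.1 does not mention masking, and 5.3.2.1 takes no difference, so they do not together spell out one procedure from which 6.1.1 alone departs. Since the improvement wording also appears in the Synopsis, Table 1 and section 6, editing 6.1.1 alone would leave the ambiguity.
- The first step of 6.1.1 is itself masked.
- The final plan under 7.1 could set a rule. However, data lock may come after grading. A late rule could restore signs if the reviewers' orderings were recorded, but it could not undo disclosure or recover separate scores.
- Lesion counts give some check on direction: "The principal investigator or an appropriately trained designee will perform a lesion count at all visits", and 5.3.2.1 has the independent reviewers count lesions too. Subjects also rate themselves on the GAIS. None of these corrects the primary score.
- This is described as a pilot study, and its primary endpoint has no concurrent control.

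**Conclusion.** The mismatch between 3.1 and 6.1.1 and the missing wrong-order rule are established on the text. The bias is conditional. It needs grades kept in the reviewer's order, and worsened pairs mis-sorted more often than improved ones. With d=0, or with the difference taken by actual visit, there is no upward bias. At d=0.5 the spurious gain is 0.15 to 0.35 grade, with the false-rejection rates in the table. These figures rest on assumed p and d and vary strongly with n.

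A reader might infer that the procedure could make an ineffective treatment succeed. The documents do not support that: success also needs a 2-point mean, which the artefact did not reach when there was no true change. A reader might also infer that the missing rule decides success on its own. For example, if every subject truly improved by exactly 2 points and 10% of pairs were mis-ordered, the mean would be 2.0 with magnitudes kept, 2 × 0.9 = 1.8 with those pairs set to zero, and 2 × (1 − 0.2) = 1.6 with them counted as −2. That is a knife-edge case, and the documents give neither an expected change nor a mis-sorting rate to make it likely.

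At risk are the supporting test and the reported effect size. This should be fixed; confidence in the practical size of the effect is medium.

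**What to change.** Before photographs go to reviewers, rewrite 6.1.1 and conform the Synopsis, Table 1 and the opening of section 6. Suggested text:

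*Each reviewer assigns a GAAS severity score to each visit's image set (baseline, visit 5, follow-up), presented in random order under a neutral code without date or visit. After all scores are locked, codes are linked to actual visits and follow-up minus baseline is computed.*

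Any before/after sorting should be done only after scores are locked, as a check on blinding. Recoding is a safeguard: 5.1.2 says of stored photographs that "they will be labeled and numbered by date with the patient ID only", and the sample file name in 5.2.1.2 carries the visit, although no section says that reviewers receive either.

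If pairwise grading is kept, use a signed scale that can record worsening, state that the true order is not disclosed before grading, and restore the sign by actual visit. Sign restoration fails if worsening can only be recorded as zero. Correcting the count of two photographs is editorial.

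**Cost.** A revised reviewer form, recoded image files and more reviewer time: 20 × 3 = 60 scores per reviewer for 20 completers, up to 50 × 3 = 150 for 50 subjects. The views forming a scored set must also be defined, since 5.2.1.2 yields 3 × 4 = 12 Visia images plus 3 DSLR views per photographed visit. The photographs and reviewers stay the same. Section 3.7 sends photographs out at the end of the study, so no data are lost if the change is made before then.

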6.2 Subject self-assessment

The subject's overall satisfaction with treatment outcome, will be recorded at visit 6. The self-assessment will be based on a 5-point Likert scale (Subject Satisfaction Assessment Scale). Subjects will also rate their improvement using the Global Aesthetic Improvement Scale (GAIS) and their quality of life using the Acne-Related Quality of Life Questionnaire.

6.3 Safety

6.3.1 Immediate/short term response

Immediate response (pain during treatment, hemorrhage, burn, erythema, edema, etc.) of the skin will be assessed by the principal investigator or qualified designate within 30 minutes post treatment by a 4 level scale: (0) None / (1) Mild / (2) Moderate / (3) Severe.

Short-term response (dryness, sloughing/flaking etc.) of the skin may develop following each treatment which is expected to resolve within several days. These responses are not considered as adverse events since they are expected outcomes related to the treatment. However, if the principal investigator determines that the severity or duration of the short-term response is abnormal, then it will be documented as an adverse event. Again, for purposes of completeness, this information will be documented in the relevant CRF of the next visit.

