procedure. At the first treatment visit, the investigator will collect demographic and medical information and perform 3 test spots to evaluate skin sensitivity and choose appropriate presets. Subjects with skin type IV-V will be monitored 48-96 hours after the test spot for their skin reaction. Subjects that demonstrate excessive skin reaction to the test spot will be withdrawn from the study and will not be included in the study efficacy population or in the safety analysis since study treatment has not occurred. Should a subject (or the subject's legally authorized representative) decide to voluntarily withdraw, all efforts will be made to collect and report the final visit observations, and the reasons for withdrawal, as thoroughly and timely as possible. Withdrawals will be documented in the CRF and reported to local institutional review board (IRB) or ethical committees as required. The first treatment visit may occur on the same day as the screening visit but can be scheduled up to 30 days after the screening.

The duration of the treatment session will be approximately 40 minutes depending on the treated area size. Expected immediate response includes temporary mild to moderate erythema and/or edema. Skin safety assessments will be conducted by the investigator after each treatment session and at follow-up visits. Photography will be conducted at baseline, the beginning of last visit and at FU. The level of the subject's discomfort will be documented at the end of each treatment session. Subject satisfaction will be evaluated at FU. Evaluation by up to 3 independent reviewers will be based on before/after pictures of the baseline, before the last treatment and at the 6 week follow up visit using GAAS.

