3.3 Safety

- Safety will be evaluated based on the number and type of any adverse event recorded throughout the study. Adverse events will be reported and categorized based on severity and device-relatedness. In addition, immediate response following treatment associated with various settings (e.g., erythema, edema, purpura, etc.), although expected results of treatment that are not considered adverse events, will be collected and reported for purposes of completeness. Information will also be captured on the intensity of response and the time required for resolution.

3.4 Study duration:

Duration of subject's participation: Up to 11 weeks from enrollment to termination (see Figure 1).

Study duration for entire study sample: Estimated to be 16 months from enrollment of first subject to the termination of the last. This is based on estimate of 8 months for recruitment + 2 months subject participation + 1 months collecting data.

Figure 1: Subject Participation

Time Intervals		1 week	1 week	1 week	1 week	6 weeks
	Enrollment	Treatment 1	Treatment 2	Treatment 3	Treatment 4	Follow-up
Timeline	Screening	Week 1	Week 2	Week 3	Week 4	Week 10

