6.3.2 Adverse events

Adverse events will be assessed throughout the duration of the study. All adverse events will be categorized with respect to severity and device-relatedness.

The following skin reactions are an expected outcome related to treatment:

- Dryness
- Sloughing/flaking of skin
- Infection
- Presence of prolonged erythema
- Presence of prolonged edema
- Burn / Blistering
- Hyperpigmentation
- Hypopigmentation
- Contact dermatitis
- Pruritus/Scarring
- Herpes simplex virus outbreak

Reports of all adverse events by subjects and investigator will be documented in the source documents and will be recorded in the Adverse Events form.

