8.1.5 Anticipated Outcome Related Adverse Events

Anticipated adverse events in this study may include: Irritation, blistering, temporary skin color changes, burns, excessive edema or erythema (excessive consider as edema or erythema that do not resolve within 2-3 days), infection, PIH (post inflammatory hyperpigmentation) and scarring. If any antibiotic ointment will be required during the study it will be provided by the study doctor at no cost.

Any anticipated AE that occurs at any time during or after the use of the study device must be reported by the Investigator to Venus Concept. If the anticipated AE, in the opinion of Venus Concept or the Investigator, is likely to affect the safety of the subjects or the conduct of the study, the IRB/ Helsinki/ other ethic committee will be notified of the effect within 10 working days after Venus Concept first receives notice of it. In this study if an adverse event of PIH occurs during the course of the 3 month follow-up period the Investigator will continue following the subject until the PIH is resolved or up to 3 months following the last treatment, whichever comes first.

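### A burn seen straight after treatment is not an adverse event under sections 3.3 and 6.3.1 but a reportable one under 8.1.5, so the AE-based safety endpoint has no single counting rule

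*Combined protocol and SAP*

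**What the plan says.** The safety endpoint is in section 3.3: "Safety will be evaluated based on the number and type of any adverse event recorded throughout the study". The same paragraph sets immediate responses apart, as "although expected results of treatment that are not considered adverse events, will be collected and reported for purposes of completeness". Its own examples are erythema, edema and purpura, left open-ended, and it asks for intensity and time to resolution.

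Section 6.3.1 says what an immediate response contains: "Immediate response (pain during treatment, hemorrhage, burn, erythema, edema, etc.) of the skin will be assessed", on a four-level scale from none to severe, within 30 minutes of treatment. Section 5.2.3.2 repeats burn and hemorrhage in the tolerability examination. Section 6.3.1 then turns to short-term responses, with dryness and flaking as examples, and continues: "These responses are not considered as adverse events since they are expected outcomes related to the treatment". An investigator who finds the severity or duration of a short-term response abnormal records it as an AE. No such clause is written for immediate responses.

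Section 6.3.2, headed as adverse events, opens a list of 11 bullets with "The following skin reactions are an expected outcome related to treatment". The list includes infection, burn or blistering, pigment change and scarring. The section closes by requiring all AEs to go on the AE form.

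Section 8.1 defines an AE broadly, as any undesirable clinical occurrence. Section 8.1.5 says: "Anticipated adverse events in this study may include: Irritation, blistering, temporary skin color changes, burns", and goes on to excessive edema or erythema, infection, post-inflammatory hyperpigmentation and scarring. The investigator must report any of these to the sponsor.

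**The concern.** A burn is one of the central harms of a device that works by light and heat, and section 8.3.1 itself names burns among the risks. If the endpoint is a count of AEs, the protocol must say whether a burn seen within half an hour of treatment is one. It gives two answers and does not say which section prevails.

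Sites could then classify the same finding differently and each point to protocol text in support. The AE rate would partly reflect which section a site read, and any error from following 3.3 and 6.3.1 runs towards too few AEs. Section 7.4 intends to judge whether the study meets its safety criteria, so the count will be used, although no numerical safety criterion is given.

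**Working it through.** The protocol states no figure on this point, so the check sets the sections side by side.

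**Status of each reaction**

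| Reaction | Named immediate response (6.3.1), hence not an AE under 3.3 | On the 6.3.2 expected-outcome list | Anticipated AE in 8.1.5 | Result |
|---|---|---|---|---|
| Burn | Yes | Yes | Yes | Direct contradiction |
| Hemorrhage | Yes | No | No | Conflicts only with the general definition in 8.1 |
| Infection | No | Yes | Yes | Ambiguous label, never declared a non-AE |
| Scarring | No | Yes | Yes | Ambiguous label, never declared a non-AE |

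Only burn appears in all three places.

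**Is there a route back to AE status?** In 6.3.1 the upgrade applies to short-term responses, rests on the investigator's judgement and has no threshold. For an immediate burn or hemorrhage, even one graded severe, section 6.3.1 provides none. The only route is to follow 8.1 or 8.1.5 in place of 3.3.

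**How far does the expected-outcome label reach?** Of the 11 bullets in 6.3.2, at least six have a counterpart in 8.1.5: infection, prolonged erythema, prolonged edema, burn or blistering, hyperpigmentation and scarring. The first two bullets, dryness and flaking, are the examples that 6.3.1 excludes from AEs on nearly the same ground of being expected. One label therefore covers both reactions declared not to be AEs and reactions that must be reported as AEs.

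**Time limits.** Section 6.3.1 expects short-term responses to resolve within several days, and 5.2.1.3 says the same of purpura. Section 8.1.5 calls erythema or edema excessive if it has not resolved in 2-3 days. The boundary between a response and an AE therefore differs by section.

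**Size, by illustration.** Enrolment is up to 50 (section 4.1), and the synopsis wants 20 to complete with the amended treatment parameters. Each subject whose only AE is an immediate burn shifts the proportion with an AE by 1/50 = 2 percentage points, or 1/20 = 5 points among 20 completers. The number of burns below is an assumption; the documents give none. Intervals are two-sided 95% Clopper-Pearson: for x of n, the limits are the 2.5% point of Beta(x, n−x+1) and the 97.5% point of Beta(x+1, n−x).

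| Subjects with an immediate burn, of 50 (assumed) | Counted as AEs (8.1.5) | Not counted (3.3 and 6.3.1) |
|---|---|---|
| 1 | 2% (0.1% to 10.6%) | 0% (upper limit 7.1%) |
| 2 | 4% (0.5% to 13.7%) | 0% (upper limit 7.1%) |
| 4 | 8% (2.2% to 19.2%) | 0% (upper limit 7.1%) |

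For 0 of 50 the upper limit is 1 − 0.025^(1/50) = 7.1%. The right-hand column is the extreme case, in which every site leaves out every burn.

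**The case against.** The strongest reply is that the protocol, read as a whole, does capture these harms. Immediate responses are graded at all four treatment visits and reported under safety, so a burn would appear in the results, if perhaps in another table. Section 8.1 sends any AE or complication during or after treatment to the AE form. Section 8.2.1 requires serious AEs to be reported whether or not expected. Section 3.3's own examples of an immediate response do not include burn. All of this stands: it rules out lost data and lowers the severity. It does not remove the conflict, because 6.3.1 puts burn inside the category that 3.3 excludes.

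Several stronger readings are tempting, and the documents do not support them.

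- A reader might take the sentence "These responses are not considered as adverse events since they are expected outcomes related to the treatment" to exclude burns. It directly follows the sentence on dryness and flaking, and the next one again concerns short-term responses. The explicit exclusion of immediate responses is in 3.3.
- A reader might infer that infection and scarring are declared not to be AEs. They are not: they sit under the adverse-event heading in 6.3.2, where expected can be read as anticipated, and 8.1.5 requires them to be reported. The risk is that a site carries the reasoning of 6.3.1 over to that list.
- A reader might say that 8.1.5 contradicts 6.3.1 on hemorrhage. Hemorrhage is in neither 8.1.5 nor 6.3.2, so its conflict is with the definition in 8.1.
- A reader might think section 3 confines the expected response to mild or moderate erythema and edema. Its wording is "Expected immediate response includes temporary mild to moderate erythema and/or edema", which is not exhaustive, and 3.3 and 5.2.1.3 also treat purpura as expected.
- A reader might fear a biased AE comparison between combination and IPL alone. None is planned: 3.2 compares the primary and secondary endpoints, section 6 calls it an efficacy comparison, and safety stands apart.

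**Conclusion.** The inconsistency is real but narrower than the full list of reactions might suggest. It is a direct contradiction for an immediate burn, a conflict with the general AE definition for hemorrhage, and an ambiguity of label for infection, pigment change and scarring.

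The consequence is misclassification and possible under-counting in the AE endpoint, with sites free to differ. The actual size cannot be known from the documents; it depends on how many immediate burns occur and how sites classify them. At 2 points per subject in a study of at most 50, even a few would be visible.

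This should be fixed, but it does not defeat the study. The trial is a pilot with no stated safety threshold that a reclassified burn would cross, and the graded responses remain available.

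**What to change.** Reconcile sections 3.3, 6.3.1, 6.3.2, 8.1 and 8.1.5 into one AE counting rule:

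1. Expectedness is recorded as an attribute of an AE and is not a reason to leave it out.
2. Burn or blistering and hemorrhage recorded as an immediate response, and every reaction listed in 8.1.5, are counted in the AE table.
3. The non-AE category is kept for the transient responses that the protocol itself describes as expected: temporary erythema and edema, purpura, dryness and flaking. Leaving out purpura would create a new conflict with 3.3 and 5.2.1.3.
4. The time limits in 5.2.1.3 and 6.3.1 on one side and 8.1.5 on the other are reconciled, so that the point at which a response becomes an AE is written once.
5. The graded immediate responses are tabulated beside the AE table, by treatment group, as a description.

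The cost is protocol wording and CRF guidance. The data are already collected. The reported AE count may be higher.
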